### **12.3 AMC Policy for Monitoring of Phase I and Phase II Trials**

This protocol will follow the AMC's policy for data monitoring (see Appendix XVI, Data Safety and Monitoring Plan).

## **13.0 ETHICAL AND REGULATORY CONSIDERATIONS**

(See Appendix IV, Informed Consent)

### **13.1 Informed Consent**

The principles of informed consent described in Food and Drug Administration (FDA) regulations (21 CFR part 50) must be followed. IRB approval of the protocol and the informed consent form must be given in writing.

The sponsor must receive a copy of the letter of approval from the IRB, which specifically approves the protocol and informed consent, before patient enrollment. The IRB must also approve any significant changes to the protocol and documentation of this approval must be sent to the sponsor. Records of all study review and approval documents must be kept on file by the Investigator and are subject to FDA inspection during or after completion of the study. AEs must be reported to the IRB. The IRB should receive notification of completion of the study and final report within 3 months of study completion and termination. The Investigator will maintain an accurate and complete record of all submissions made to the IRB, including a list of all reports and documents submitted.

### **13.2 Changes To The Protocol**

Any change or addition to this protocol requires a written protocol amendment that must be approved by Novartis, CTEP and the Investigator before implementation. Amendments significantly affecting the safety of subjects, the scope of the investigation or the scientific quality of the study, require additional approval by the IRB/IEC/REB. A copy of the written approval of the IRB/IEC/REB must be sent to Novartis. Amendments affecting only administrative aspects of the study do not require formal protocol amendments or IRB/IEC/REB approval but the IRB/IEC/REB of each center must be kept informed of such administrative changes.

### **13.3 Women And Minorities**

This is a study being conducted by the NCI-sponsored AIDS Malignancy Consortium (AMC). As part of their contractual obligations, each participating site within the AMC, and the AMC as a whole, is required to assure that the participation of women and minority subjects reflects the percentage representation of these populations in their geographic region and, for the AMC, the United States as a whole. As such, it is expected that the representation of subjects on this trial will reflect the constitution of the respective populations.

## APPENDIX I: SCHEDULE OF EVENTS

Assessment	Eligibility/ Screening	Baseline	D 1	D 2	D 8	D 15	D 16	D 29 (and then every 28 days thereafter)	D 56 (and every two months thereafter)	Every 3 months thereafter	Treatment Discontinuation
Clinical Studies											
Informed Consent	X										
KS Documentation	X 										
HIV Documentation	X 										
Medical History	X 										
Physical Exam: Vital signs, height, weight, KPS	X 		X		X	X		X			X
Signs and Symptoms Review	X 		X		X	X		X			
KS Tumor Assessment			X 					X 	X 		X
KS Staging	X 										
Concomitant Medication Review	X 		X		X	X		X			
Adverse Events					X	X		X			X
Chest x-ray	X 										
Laboratory Studies											
CBC with differential and platelets	X 		X		X	X		X			X
Serum Chemistries 	X 		X		X	X		X			X
Urine Phosphate and Creatinine	X 		X		X	X		X			X
CD4 count		X 						X 		X	X
Serum beta HCG pregnancy test	X 										
HIV plasma RNA		X 						X 		X	X
HHV-8 Viral Load			X			X 					X
Stool Guaiac	X 										
Serum/plasma for cytokine profile		X			X			X 			
Pharmacokinetics 			X	X		X	X				
ACSR Donation		X									
Biopsy for receptor phosphorylation		X			X						
Biopsy for mutation receptor		X 									X

1. Anytime prior to study entry.
2. Done within 4 weeks of study entry, if positive x-ray, a chest CT will be performed
3. Serum Chemistries: Liver enzymes (SGOT, SGPT, alkaline phosphatase), BUN, creatinine, electrolytes, amylase, bilirubin (direct and indirect) and phosphate. 25-Hydroxyvitamin D is measured at baseline.
4. To be done within 72 hours of study entry and anytime pregnancy is suspected
5. To be done within 4 weeks of study entry.
6. Collect on the first 12 patients: 0 (immediately prior to the patient taking meds for that day), 0.5, 1, 2, 3, 4, 8, and 24 (immediately prior to the next day's dose) hours.
7. To be done at baseline, D29, D56 and every 2 months thereafter.
8. Within 2 weeks prior to study entry.
9. To be obtained within 21 days prior to study entry.
10. To be performed on Day 1 prior to receiving study medication but may not be performed earlier than within 2 weeks of initiating treatment.
11. To be performed at baseline and time of progression or treatment discontinuation.
12. Day 29 only.
13. Day 29 and every 3 months thereafter.
14. To be collected on Day 1 and Day 15 of cycle 1 and on Day 1 of cycles 3, 5, 7, 9, and 11.

## **APPENDIX II: DEFINITION OF AIDS INDICATOR CONDITIONS**

- Aspergillosis, invasive \*
- *Bartonella henselae* infection, disseminated (bacillary angiomatosis, peliosis hepatis) \*
- Candidiasis of bronchi, trachea, or lungs \*
- Candidiasis, esophageal \*
- Cervical cancer, invasive \*
- Coccidioidomycosis, disseminated or extrapulmonary \*
- Cryptococcosis, extrapulmonary \*
- Cryptosporidiosis, chronic intestinal (> 1 month's duration) \*
- Cytomegalovirus disease, invasive \*
- Cytomegalovirus retinitis \*
- Encephalopathy, HIV-related \*
- Herpes simplex: chronic ulcer(s) (> 1 month's duration), bronchitis, pneumonitis, or esophagitis \*
- Histoplasmosis, disseminated or extrapulmonary \*
- Isosporiasis, chronic intestinal (> 1 month's duration) \*
- Kaposi's sarcoma (progression to visceral disease)
- Lymphoma, Burkitt's (or equivalent term) \*
- Lymphoma, immunoblastic (or equivalent term) \*
- Lymphoma, primary, of brain \*
- Microsporidiosis, diarrhea > 1 month or disseminated \*
- *Mycobacterium avium* complex or *M. kansasii*, disseminated or extrapulmonary \*
- *Mycobacterium tuberculosis*, any site (pulmonary or extrapulmonary) \*
- *Mycobacterium*, other species or unidentified species, disseminated or extrapulmonary \*
- Nocardiosis, pulmonary, brain or disseminated \*
- *Pneumocystis carinii* pneumonia (new or recurrent diagnosis)
- Progressive multifocal leukoencephalopathy \*
- *Salmonella* septicemia, recurrent \*
- Toxoplasmosis of brain \*
- Wasting syndrome due to HIV \*

\* New Diagnosis

### **APPENDIX III: CRITERIA FOR ACCEPTABLE AIDS DEFINING EVENTS**

1. Microbiologically- or histologically-confirmed AIDS-related opportunistic infection;  
  
OR
2. Presumptive diagnosis of CMV retinitis, confirmed by an ophthalmologist, or of CNS toxoplasmosis or CNS lymphoma by accepted imaging technique;  
  
OR
3. Biopsy-proven AIDS-related malignancy. For the purposes of the protocol, only the development of visceral disease will constitute a KS endpoint;  
  
OR
4. Physician-documented HIV-1 Cognitive Motor Complex (dementia) or HIV wasting syndrome;  
  
OR
5. Presumptive diagnosis of PCP as determined by the following:
  - Compatible symptomatology (e.g., fever, cough, shortness of breath).
  - Compatible chest x-ray.
  - $pO_2 < 85$ .
  - Absence of other pathogens on sputum examination.
  - Negative blood cultures.
  - Response to appropriate anti-Pneumocystis therapy.

NOTE: For the purposes of this protocol, a primary study endpoint will be defined as:

- A new AIDS defining event, OR
- Recurrent PCP, OR
- Death.

## APPENDIX IV: KARNOFSKY PERFORMANCE SCALE

Description	Percent	Karnofsky Performance Scale
Able to carry on normal activity; no special care needed	100	Normal: no complaints: no evidence of disease
	90	Able to carry on normal activity; minor signs or symptoms of disease
	80	Normal activity with effort: some signs or symptoms of disease
Unable to work, able to live at home and care for most personal needs: a varying amount of assistance is needed	70	Cares for self, unable to carry on normal activity or to do active work
	60	Requires occasional assistance but is able to care for most of needs
	50	Requires considerable assistance and frequent medical care
Unable to care for self; requires equivalent of institutional or hospital care: disease may be progressing rapidly	40	Disabled: requires special care and assistance
	30	Severely disabled: hospitalization is indicated although death is not imminent
	20	Very sick: hospitalization necessary; active supportive treatment is necessary
	10	Moribund: fatal processes progressing rapidly
	0	Dead

**APPENDIX V: RECOMMENDED STAGING CLASSIFICATION FOR  
KAPOSI'S SARCOMA**

	GOOD RISK (0) (All of the following)	POOR RISK (1) (Any of the following)
Tumor (T)	- Confined to skin and/or lymph nodes and/or minimal oral disease 	- Tumor-associated edema or ulceration - Extensive oral KS - Gastrointestinal KS - KS in other nonnodal viscera
Immune system (I)	- CD4 cells $\geq$ 200/ $\mu$ L	- CD4 cells < 200/ $\mu$ L
Systemic illness (S)	- No history of OI or thrush - No "B" symptoms  - Performance status $\geq$ 70 (Karnofsky)	- History of OI and/or thrush - "B" symptoms present - Performance status < 70 - Other HIV-related illness (e.g., neurological disease, lymphoma)

T0 = tumor confined to skin, lymph nodes and/or minimal oral disease.

T1 = any tumor falling under the "Poor Risk" criteria.

S0 = no history of OI or thrush, no "B" symptoms, and Karnofsky Performance status  $\geq$  70.

S1 = any "Poor Risk" systemic illness signs and symptoms.

NOTE: Staging criteria taken from: Krown SE, Metroka C, Wernz JC. Kaposi's sarcoma in the acquired immunodeficiency syndrome: A proposal for uniform evaluation, response, and staging criteria. J Clin Oncol 1989;7:1201-1207. This criteria was adopted by the ACTG Oncology Committee.

Minimal oral disease is nonnodular KS confined to the palate.

"B" symptoms are unexplained fever, night sweats, > 10% involuntary weight loss, or diarrhea persisting more than 2 weeks.

**A. COLLECTION**

Consent patient for ACSR donation. Collect **20 cc** of whole blood in ACD tubes.

**B. SHIPPING**

To ship bloods, place the tubes into a canister of a STP-100 SAF-T-PAK shipper wrapping each tube in bubble wrap and using the absorbent paper at the bottom of the canister. Mailers for shipping donations will be supplied by the ACSR upon request. Please allow a few days for receipt of the mailers. Each sample tube should be labeled using a sharpie pen with the following information:

- Protocol #: AMC 042
- 9 digit Patient #
- Date and time of collection
- Specimen type, i.e., **WB**=Whole Blood, **P**=Plasma, **S**=Serum
- Specimen purpose: Donation

Place the lid on the canister and place it inside of the ambient SAF-T-PAK shipper. **Fold and pack ACSR form inside shipping box.** Seal the ambient shipper with cellophane shipping tape. Label the ambient shipper with the "Infectious substance" diamond shaped label. On one side, in black marker write "BIOLOGIC SUBSTANCE, CATEGORY B", your name or name of responsible person, date of collection and phone number of the person responsible for the package.

## **B.2 Instructions for Specimens Collected on Friday**

### PREPARATION OF PLASMA AND MONONUCLEAR CELLS

It is preferable that separation occurs as soon as possible. If necessary, whole blood in acid citrate dextrose (yellow top tube) can be held at room temperature for no more than 24 hours.

#### Materials:

Lymphocyte Separation Medium (LSM Solution, Ficoll-Hypaque - sterile)

15 ml conical centrifuge tubes (sterile)

PBS (sterile)

1, 5 ml and 10 ml serologic pipettes (sterile)

NUNC tubes

Alcohol-saturated, control rate freezer container

DMSO freezing media:

- 50% Cryoprotective Medium, Cambrex (catalog no.: 12-132A)
- 50% Heat Inactivated Fetal Bovine Serum

1. Preparation of Plasma Samples
  - a. The 7 ml tube of whole blood in acid citrate dextrose should be rotated gently 2 or 3 times before being centrifuged. Do not transfer before centrifugation.
  - b. The cells are separated by centrifugation at 500 g for 10 minutes.
  - c. 0.5ml aliquots of plasma are removed and put into 1.5 ml screw top tubes and transferred to liquid nitrogen storage.
  
2. Peripheral Blood Mononuclear Cell Separation and Freezing
  - a. The cells and plasma remaining from the previous step are transferred into a 15 ml conical tube, capped and re-suspended by gently tapping the bottom of the tube.
  - b. Sterile PBS should be added to the suspended cells until the final volume is 8 ml; invert to mix.

- c. The 8 ml whole blood-PBS mixture should be carefully overlaid onto 4 ml of room temperature LSM or Ficoll-Hypaque solution in a sterile 15 ml conical tube. A sharp interface should exist between the LSM and the whole blood mixture. (If the layer of LSM gets mixed with the blood-PBS, the tube should be gently rotated to mix the blood, PBS, and LSM, and transfer to a 50 ml sterile conical tube. An equal volume of PBS is added, and the cells are separated at 600 g for 15 minutes. After removal of LSM-PBS supernatant, return to Step b).
- d. The 15 ml conical tube for 30 minutes at 900 g at room temperature. The mononuclear leukocytes (principally lymphocytes and monocytes) will band at plasma/LSM interface.
- e. The fluffy white layer just below the plasma layer should be aspirated off, along with approximately half of the LSM layer under it, and transferred to an appropriately labeled 15 ml sterile conical centrifuge tube. Mix by gentle rotation.
- f. Washed twice in sterile PBS - centrifuge at 500 g for 10 minutes.
- g. Cell pellet should be mixed well with a gentle finger-tapping action.
- h. Using a 1 ml pipette, the \*DMSO freezing mixture should be added drop wise to the cell pellet suspension. Gently finger-tap between drops. If the cell pellet is small, only 1 ml of freezing media is added (and only one aliquot of cells is frozen). If the cell pellet is large, up to 4 ml of freezing media can be added in a drop wise fashion. (Cell densities of 1 - 10 million PBMC/ml are best for cryopreservation. If a hemocytometer is available, the optimal concentration is 5 million PBMC/ml).

**\*Important-Do not put the DMSO containing media on the cell button all at once.**

3. Freeze the cell suspension in 0.5 ml aliquots in sterile NUNC vials by placing the NUNC tubes in a room temperature, alcohol saturated, control rate freezer container and store in the -80°C freezer overnight. Transfer the cell suspension into the liquid nitrogen temperature freezer for long-term storage the next working day.

**\*\*\*PLEASE DOUBLE CHECK PACKAGING OF SHIPPER AND DO NOT DEVIATE FROM REQUESTED LABELING\*\*\***

Shipping frozen aliquots requires the use of packaging acceptable for dry ice and Class 9 label with weight of dry ice written on package

**Please Note:** The shipper will be mailed back to the AMC site.

The STP-100 SAF-T-PAK shipper is a complete kit w/all trappings, bubble wrap, absorbent paper, labels, everything (but to reuse the shipper, you will need new labels, wrap, etc).

### **B.3 Record of Specimens**

This study will track specimens via GlobalTraceSM, a component of the AMC AdvantageEDCSM system. The GlobalTrace shipment manifest must accompany all specimen shipments.

## **APPENDIX IX: PUNCH BIOPSY**

### **EXPRESSION/ACTIVATION (PHOSPHORYLATION) IMATINIB TARGETS AND SIGNALING INTERMEDIATES**

#### **A. METHODOLOGY**

- A.1** Biopsies will be performed with a 4 mm punch biopsy at baseline and Day 8 of treatment. Fixed tissue samples in formalin will be received from trial sites. They will be embedded in paraffin blocks with an orientation that allows for sectioning perpendicular to the skin surface. Staining of slides will be batched in order that pre and post sections are stained at the same time to control for variability. Two ribbons of four to five tissue sections 5 um thick will be placed one below the other on ProbeOn Plus slides (Fischer). The two ribbons will be treated identically except the top ribbon will receive the primary antibody and the bottom ribbon, which is serving as a negative control, will not. Slides will be stained using the following antibodies: LANA, anti-PDGF-R and anti-phospho-PDGF-R (Tyrosine 783) (Cell Signaling, Beverly, MA). H&E stains will also be performed on all pre and post specimens.
- A.2** Within 48 hours of sectioning, slides will de-paraffinized in xylene and ethanol. Antigen retrieval will be performed by boiling the slides for 10 minutes in pH 6 citrate buffer followed by 10 minutes in 3% H2O2. The slides for phospho-PDGF-R require 15 minutes in 1mM EDTA, pH 8.0 prior to H2O2. The slides are then incubated overnight with the primary antibody at a 1/100 dilution for anti-PDGF-R, a 1/100 dilution for anti-LANA, and a 1/50 dilution anti-phospho-PDGFR at 40C. The slides are then incubated for 30 minutes with 100 µL of biotinylated anti-rabbit secondary antibody, then for 30 minutes with ABC avidin/biotin (Vector Labs, Burlingame, CA) with washes in after each incubation. Slides were incubated in ethanol and xylene prior to mounting coverslips.
- A.3** All slides will be assigned a random numerical identifier and will be presented in a blinded fashion to two pathology reviewers (Drs. [name] and [name]). Based on review of the slides from the pilot study, it was determined nearly all of the KS spindle cells stained uniformly positive with minimal heterogeneity, and after treatment their immunoreactivity decreased uniformly. Staining intensity of basal keratinocytes is reduced after treatment with imatinib, precluding using them as an internal standard for assessment of lesional cell staining intensity in post-treatment samples. Immunoreactivity of lesional KS cells will thus be scored on a scale of 0 to 5+ by two pathologists, with 0 being the negative control staining of basal keratinocytes and 5+ being equal to the staining intensity of basal keratinocytes in pretreatment samples, and a final score for each sample based on the average of 4 sections.

**A.4** Analysis: Immunohistochemical methods are amenable to statistical assessment. For instance, even using an activation specific antibody, Weber and his colleagues have been able to statistically correlate erk1/erk2 activation with tumor grade and stage of prostate cancer [52]. In this study we will classify the activation of PDGF-R as low (score of 0, 1+ or 2+) or high (score of 3+, 4+ or 5+). The breakpoint for this grouping is based on our observations of degree of inhibition in the pilot trial. Biopsy pairs that score as high at baseline and low at seven days will be considered PDGF-R inhibited, and those that score as high at baseline and high at seven days will be considered PDGF-R not inhibited. Pairs that score low at baseline will be omitted from the analysis. For the purposes of Aims 2 and 3, clinical response is defined as partial or complete response and non-response will be classified as stable disease or disease progression. Our a priori hypothesis is that inhibition of PDGF-R at 7 days correlates with clinical response. A chi 2 test will be used to test whether phosphorylation of PDGF-R (low or high) at 7 days predicted clinical response.

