We examined tumor biopsies using immunohistochemistry (IHC) with phosphospecific antibodies to determine the activation status of the PDGF and c-kit pathways. A majority of protein kinases require phosphorylation of a serine/threonine or a tyrosine in the activation loop to allow kinase activity. Phosphospecific antibodies have been raised to a number of these sites and are useful as surrogate markers of activity. We used phosphospecific antibodies to PDGF-R and c-Kit as well as their downstream effectors, ERK1/ERK2 and AKT. Antibodies were used anti-c-Kit (Dako); anti-PDGF-R, anti-phospho- $\beta$ -PDGF-R (tyrosine 751), anti-phospho-AKT (serine 473) and anti-phospho-ERK (threonine 202/tyrosine 204) (Cell Signaling, Beverly, MA). We have not yet found an anti-phospho-c-kit antibody that works reliably for IHC. Six patients had evaluable baseline IHC. All six patients demonstrated constitutive expression of PDGF-R and c-Kit receptors. Four patients had biopsies at baseline and 4 weeks that were evaluable by IHC. Three of four patients demonstrated activation of PDGF-R and ERK, a downstream effector of PDGF-R and c-Kit, at baseline with inhibition of both pathways after treatment with imatinib. We also examine the activation status of AKT, a component of the PI3K pathway and downstream target of PDGF-R and c-kit. Activation of AKT was not seen at baseline or after treatment in any patients. VEGF, which has been shown to be downstream of PDGF-R

activation in culture KS spindle cells, was measured pre and post treatment but no significant changes in VEGF concentrations were seen.

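### Appendix IX A.4 tests a graded phospho-PDGF-R score only as low/high by chi-square, which discards information, leaves averages between 2 and 3 unclassified, and can exceed nominal size at 8 v 8

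*Combined protocol and SAP*

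**What the plan says.** In Appendix IX A.3, "Immunoreactivity of lesional KS cells will thus be scored on a scale of 0 to 5+ by two pathologists", with "a final score for each sample based on the average of 4 sections". A.4 then calls whole-number scores up to 2+ low and scores from 3+ upward high. The reason given is that "The breakpoint for this grouping is based on our observations of degree of inhibition in the pilot trial". A pair that goes from high to low counts as inhibited, and one that stays high as not inhibited. "Pairs that score low at baseline will be omitted from the analysis".

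The hypothesis is stated in advance: "Our a priori hypothesis is that inhibition of PDGF-R at 7 days correlates with clinical response". The test is given in one sentence: "A chi 2 test will be used to test whether phosphorylation of PDGF-R (low or high) at 7 days predicted clinical response". No continuity correction, alpha, effect size, SD, expected number of pairs or power is given.

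Section 12.2 describes the evaluation of PDGF-R inhibition as a comparison of mutations with response, by chi-square or Fisher's exact tests. It lists no analysis of the phosphorylation score, so A.4 is the only plan for these data, and A.4 does not mention Fisher's test.

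**The concern.** PDGF-R inhibition is the first secondary objective (section 2.2.1), and patients have research biopsies at baseline and Day 8 to measure it. After the cut, a Day 8 score of 0 counts the same as 2+, while 2+ and 3+ count as opposites. With so few pairs, three things matter: how much information the cut discards, whether every score has a class, and whether the p-value means what it says. If these are left open, neither a positive nor a negative result on this hypothesis could be read with confidence.

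**Working it through.** **1. Number of pairs.** The plan gives no power for this test. Its 22 evaluable patients come from the two-stage design in section 12.1, which reproduces: P(at most 2 of 10 respond at 20%) = 0.1074 + 0.2684 + 0.3020 = 0.678 (stated 0.68); exact type I error 0.049; power at 50% 0.902 (stated 0.90). In the pilot, "Three of four patients demonstrated activation of PDGF-R and ERK" at baseline (section 1.1.5). If that share held, 22 x 3/4 = 16.5, or about 16 pairs. At a 50% response rate this is 8 v 8.

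**2. Size of the chi-square at 8 v 8.** For 6 of 8 low v 2 of 8 low, without correction: 16 x (6x6 - 2x2)^2 / 8^4 = 16 x 1024 / 4096 = 4.00, above 3.84, so significant. For 3 v 0: 16 x 24^2 / (8 x 8 x 3 x 13) = 3.69, not significant. Every table whose low counts differ by 4 or more rejects, and no others do. With no association and half the scores low, the difference plus 8 is Binomial(16, 0.5), so the size is 2 x (1820 + 560 + 120 + 16 + 1) / 65536 = 0.077. The same rule with a quarter of scores in one class gives 0.040, so the excess arises when low and high are near balance. Fisher's test needs a difference of 5: 2 x 697 / 65536 = 0.021.

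**3. Averages without a class.** Whole-number scores averaged over four sections can give 2.25, 2.5 or 2.75, which belong to neither class. If Day 8 scores are normal with SD 1 (assumed) and recorded in quarter points, the share falling there is the probability between 2.125 and 2.875. That is 0.18 at mean 1.5 and 0.29 at mean 2.5. At 8 v 8 this is 8 x 0.18 + 8 x 0.29 = 3.8, or about 4 of 16 pairs.

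**4. Power on the same 16 pairs.** All inputs are assumptions: 8 v 8, SD 1, scores in quarter points within 0 to 5, cut at 2.5, two-sided 0.05, by simulation.

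| Day 8 means, responders / non-responders | Rank-sum | Chi-square, uncorrected | Fisher |
|---|---|---|---|
| 1.5 / 2.5 | 0.41 | 0.37 | 0.18 |
| 1.25 / 2.25 | 0.40 | 0.30 | 0.13 |
| 2 / 3 | 0.41 | 0.43 | 0.23 |
| 1.25 / 2.75 | 0.74 | 0.66 | 0.42 |

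For the 1-point shifts, rank-sum minus chi-square is about -1 to +10 points, with rounding and simulation error of about 1 point. For the 1.5-point shift it is +8. Rank-sum minus Fisher is 18 to 32 points. The chi-square column is flattered by the excess size in step 2.

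**5. If most Day 8 scores are low.** This is plausible, since all three activated pilot pairs were inhibited after treatment. With overall mean 1.7, SD 1.2 and 8 v 8, rank-sum v chi-square is 0.268 v 0.221, 0.416 v 0.338, 0.543 v 0.425 and 0.742 v 0.598 for shifts of 0.8, 1.0, 1.2 and 1.5 SD. The gains are 5, 8, 12 and 14 points. For 1-point shifts at SD 1 lying further below the cut, chi-square power falls to about 0.10, while rank-sum stays at 0.39-0.42.

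**6. If the score is all-or-none.** With Day 8 scores clustered at 1 or 4 (SD 0.6), low in 80% of responders and 30% of non-responders (assumed), 8 v 8 gives chi-square 0.63, rank-sum 0.37 and Fisher 0.39.

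**The case against.** The strongest defence is that target inhibition may be close to all-or-none. A.3 reports little heterogeneity and a uniform fall in staining after treatment, and the cut comes from pilot data. Under that pattern the low/high chi-square wins (step 6). This stands as a limit on the gain. It does not settle the matter, because rank-sum and Fisher are then about equal, and the pilot is thin support for the cut. It had four evaluable pairs, biopsied at 4 weeks, with a tyrosine 751 antibody (section 1.1.5). This trial biopsies at Day 8 (section 1.2.1) with a tyrosine 783 antibody (Appendix IX A.1).

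The exclusion of low-baseline pairs is also defensible, since a receptor that is not active at baseline cannot be shown to be inhibited. This stands in full. Section 12.2 permits exact logistic regression on other covariates, so a graded analysis is not ruled out, but none is specified. The analysis is correlative and touches neither the primary endpoint nor the stopping rule.

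A reader might infer four stronger points, which the documents do not support:

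- **A loss of 11-20 points of power.** At 11 v 11, rank-sum has 0.56 and chi-square 0.36-0.45. But A.4 would run the chi-square on all 22 only if no pair were low at baseline.
- **A larger gain from testing all 22 pairs.** This assumes that low-baseline pairs carry the same signal. If six such pairs (3 v 3) have Day 8 scores near 1 unrelated to response, the rank test on all 22 has 0.26, 0.29 and 0.18 for the first three rows of the table and 0.55 for the fourth. The planned chi-square on 16 has 0.38, 0.30, 0.43 and 0.68.
- **A quarter of pairs will be lost.** Three of four has an exact 95% interval of 19-99%, and it counts activation of both PDGF-R and ERK.
- **This is the trial's only hypothesis stated in advance.** Section 1.2.2 also hypothesises that cytokines predict response.

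**Conclusion.** The point holds as a minor one. Three parts do not depend on an assumed effect: graded information is discarded, averages between 2 and 3 have no class, and an uncorrected chi-square at 8 v 8 can have a size of about 0.077. The 8 v 8 itself rests on the pilot share and a 50% response rate.

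The effect on power is modest and assumption-based. It is roughly neutral to +10 points for a rank test on the same 16 pairs with a smooth 1-point shift, larger if Day 8 scores are mostly low or the comparison is with Fisher's test, and reversed against chi-square if the score is all-or-none. Even the rank test has only about 0.4 power for a 1-point shift, so a negative result would remain weak evidence. A fixed loss of power cannot be attributed to the plan.

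**What to change.** In Appendix IX A.4:

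- Make the main test a graded one in the high-baseline pairs. Use either a Wilcoxon rank-sum test of the averaged Day 8 score (or its change from baseline) in responders v non-responders, or exact logistic regression of response on the Day 8 score with the baseline score as covariate. Name one in advance, with its alpha and sidedness.
- Use all evaluable pairs, adjusted for baseline score, only as a sensitivity analysis, because low-baseline pairs may dilute the effect.
- Keep the low/high table as a supplement, tested by Fisher's exact test, with a stated rule for averages between 2 and 3. The same rule should decide which pairs count as high at baseline.
- Refer to this analysis in section 12.2.

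The cost is a few sentences, with no new specimens, readers or assays. The downside is some loss of power if the score is truly all-or-none.
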